Visit 1 - Baseline, Day 0	0 weeks	
 ● Medical Hx ● Blood Tests ● Basic measurements (incl. height, weight, BMI, hip & waist circumference) ● Urine Sample ● Questionnaire
Visit 2	Within 35-days of Visit 1	
 ● MRI Scan ● BP (optional) ● ECHO (optional) ● Questionnaire
Visit 3	6-9 months	
 ● Medical Hx ● Blood Tests ● Basic measurements (incl. height, weight, BMI, BP) ● Urine Sample ● Questionnaire

Visit	Time	Visit Details
		
 ● MRI ● Medical Record Review

Further to this, participants will be asked to give consent to the review of their medical records at 3 time points - years 1, 3, and 5, following baseline assessment. This review will be conducted by authorised study investigators who will obtain clinical outcome measures relating to the study objectives, for example, measures of liver or kidney function.

In the majority of cases, follow-up data at years 1,3,5 will be entered from participants’ medical records. However, some participants may receive a short telephone call at years 1,3,5 to clarify any data which may be unclear or, to supply data which may be missing from their medical record. All participants recruited and scanned at Perspectum Ltd. in Oxford (a non-NHS clinical study site) will complete their years 1,3,5 follow-up medical history over the telephone: although all participants have consented to a medical records review during the study, medical records are not available to staff outwith the NHS. Thus self-reported data will be collected from these participants.

[figure not shown]

Figure 4 - Schematic of patient recruitment and study pathway (participants will be asked to confirm an absence of COVID-19 symptoms prior to each visit and may undergo a temperature measurement if necessary)

b. Study Setting

This is a multi-centre study conducted in 4 localities:

- 1) Liverpool
- 2) Oxford (Oxford University Hospitals NHS Foundation Trust - OUHNHSFT)

- 3) London (in the catchment of the Royal Free NHS Foundation Trust)
- 4) Oxford (Perspectum Ltd.)

Site 1) and 2) to recruit 50 T2D patients each, with the remaining 50 patients to be recruited between sites 3) and 4). Recruitment will be carried out from various settings to include community, primary care and secondary care diabetes clinics. Imaging will be carried out at local imaging centres for each locality.

5. Study Participants

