5.2. Exclusion Criteria

- The participant may not enter the study if they have any contraindication to magnetic resonance imaging (standard MR exclusion criteria including pregnancy, extensive tattoos, pacemaker, shrapnel injury, severe claustrophobia).
- Patients with known autoimmune hepatitis, viral hepatitis, Wilson's disease, haemoglobinopathies or significant structural renal tract abnormality.
- Patients with known excessive alcohol intake.
- Any other cause, including a significant disease or disorder which, in the opinion of the investigator, may either put the participant at risk because of participation in the study, or may influence the participant's ability to participate in the study.

6. Sample size

The primary endpoint of the study is to compare the MRI metrics for liver fibroinflammation in those patients with type 2 diabetes at baseline vs. individuals who are healthy and non-diabetic. Values for the healthy, non-diabetics will be provided from data from the UK Biobank (UKBB)(30) or from other studies (31). Healthy individuals will be matched to the diabetic population based on gender, age and ethnicity. Analysis will be based on a two-sample, two-sided t-test.

The sample size required to perform a t-test with 90% power and alpha of 0.05 would require n=150. Based on MRI metric for liver fibroinflammation (cT1) this assumes:

- Detection of a 24.87 ms difference in cT1 in liver (This represents 50% of the difference in cT1 between self-reported diabetes vs healthy subgroups within the UK Biobank), based on unpublished data from Perspectum)
- SD of 42ms (pooled SD from self-reported diabetes and healthy subgroups within UKBB, based on unpublished data from Perspectum)
- 20% drop-out rate.

Secondary endpoints of the study include separate comparisons of MRI metrics for liver fat infiltration and volume in patients with type 2 diabetes vs. the same metrics in healthy, non-diabetic individuals. Values for the healthy, non-

diabetics will be provided from data from the UK Biobank (30) or or from other studies (31) and will be selected based on the matching of gender, age, ethnicity to the patients from this study with type 2 diabetes. Analysis will be based on two-sample, two-sided t-tests.

Based on MRI metric for liver fat infiltration (PDFF), the sample size required to perform the t-test with 90% power and alpha of 0.05 would require n=150. This assumes:

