- Detection of a 2.4% difference in PDFF [This represents 63% of the difference in PDFF between self-reported diabetes vs healthy subgroups within UK Biobank, unpublished Perspectum]
- Measurement SD of 5.4% (Pooled SD from self-reported diabetes and healthy subgroups within UK Biobank, based on unpublished data from Perspectum)
- 20% drop-out rate.

Based on MRI metric for liver volume, the sample size required to perform the t-test with 90% power and alpha of 0.05 would require n=150. This assumes:

- Detection of a 0.084 L difference in liver volume in liver (This represents 6% of the pooled mean from UK Biobank data, unpublished Perspectum)
- Measurement SD of 0.289 L (pooled mean from UK Biobank data, unpublished Perspectum)
- 20% drop-out rate.

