7.3.3. Withdrawing from the study

Each participant has the right to withdraw from the study at any time. In addition, the Investigator may discontinue a participant from the study at any time if they deem it necessary for reasons that might include:

- Ineligibility (arising during the study)
- Significant protocol deviation
- Significant non-compliance with study requirements
- Withdrawal of consent
- Loss to follow up

Data already collected from the study participants will be included in the analysis. Withdrawn participants will be replaced. The reason for withdrawal (if provided) will be recorded in the CRF.

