The results will be expressed as effect sizes and 95% confidence intervals (95% CI). Spearman and/or Pearson’s correlations will be calculated to test associations between categorical and / or continuous variables, for example significant correlations between MRI metrics and weight, and between MRI metrics and biochemical metrics. To determine the diagnostic utility of MRI in these cohorts for assessing organ dysfunction, receiver-operating characteristic analyses will be carried out.

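### Section 6 states the same n=150 at 90% power for three liver effects that differ two-fold, with no control number; at 1:1 matching, liver volume has 61% to 71% power

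*Protocol*

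**What the plan says.** Protocol Section 6 bases all three calculations on a two-sample, two-sided t-test at alpha 0.05, each with 20% drop-out.

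- **cT1 (primary):** "The sample size required to perform a t-test with 90% power and alpha of 0.05 would require n=150", for a difference of 24.87 ms and an SD of 42 ms.
- **PDFF (secondary):** the same n is stated for "liver fat infiltration (PDFF), the sample size required to perform the t-test with 90% power", with a difference of 2.4% and an SD of 5.4%.
- **Liver volume (secondary):** "liver volume, the sample size required to perform the t-test with 90% power and alpha of 0.05 would require n=150". The inputs are "Detection of a 0.084 L difference in liver volume in liver", described as 6% of the pooled mean, and "Measurement SD of 0.289 L (pooled mean from UK Biobank data, unpublished Perspectum".

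Controls are matched individuals taken from UK Biobank or other studies. Neither Section 6 nor Section 10.2 gives their number or a ratio. The Synopsis and Section 4.b make 150 the number of recruited patients with type 2 diabetes: "Site 1) and 2) to recruit 50 T2D patients each, with the remaining 50 patients to be recruited between sites 3) and 4". Section 7.3.3 adds: "Withdrawn participants will be replaced".

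**The concern.** For a given power, alpha, control ratio and drop-out rate, the required n is proportional to the inverse square of the standardised effect. The effects here differ two-fold, yet the n, the power, the alpha and the drop-out are identical. At most one of the three statements can be an exact requirement. Because 150 is stated as the requirement for each metric, the claim fails wherever the true requirement is larger, and liver volume is the exposed one.

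What is at stake is a formal 90% power claim for a named secondary endpoint. A reader who trusts it could take a non-significant liver-volume result as good evidence against a 0.084 L difference, when the comparison may have had far less power than stated.

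**Working it through.** **Inputs (Section 6).** Two-sided alpha 0.05, power 90%, drop-out 20%. Standardised effects d = difference / SD:

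- cT1: 24.87 / 42 = 0.592
- PDFF: 2.4 / 5.4 = 0.444
- Liver volume: 0.084 / 0.289 = 0.291

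The ratio of largest to smallest is 0.592 / 0.291 = 2.04, so required n differs by about 2.04² ≈ 4.15 at any fixed control ratio.

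**Required n at 1:1.** Normal approximation: n per group = 2(1.960 + 1.282)² / d². The next column uses the non-central t distribution, and the last divides it by 0.8 for drop-out.

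| Metric | Normal approx. | Non-central t | After 20% drop-out |
|---|---|---|---|
| cT1 | 59.9 | 61 | 77 |
| PDFF | 106.4 | 108 | 135 |
| Liver volume | 248.7 | 250 | 313 |

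**Trying to reproduce 150.**

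- cT1: 60 + 60 = 120, and 120 / 0.8 = 150. This works only if 150 is the total of both groups, whereas the Synopsis and Section 4.b make it the number of patients alone.
- Liver volume: with effectively unlimited controls, n = (1.960 + 1.282)² / 0.291² = 124.4, so 125 patients, and 125 × 1.2 = 150. The usual inflation, dividing 124.4 by 0.8, gives 156. The same unlimited-control convention with division by 0.8 gives 38 for cT1 and 68 for PDFF.
- No convention tried gives 150 for all three.

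If 150 did count both groups, liver volume would have 35% power (60 v 60) or 42% (75 v 75).

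**Power with 150 as the patient number (non-central t).** The evaluable number is either 120 (150 × 0.8) or 150 (withdrawals replaced). The control ratio is an assumption and is varied. At 1:1, cT1 has 99.5% (120 per group) or 99.9% (150 per group), and PDFF has 92.9% or 97.0%. For liver volume:

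| Controls per patient | 120 evaluable | 150 evaluable |
|---|---|---|
| 1 | 61.1% | 70.9% |
| 2 | 73.7% | 82.7% |
| 4 | 81.2% | 88.9% |
| 5 | 82.7% | 90.1% |
| Unlimited | about 89% | about 94.5% |

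With 120 patients and 150 controls, power is 65.7%. With 150 evaluable patients, 90% is reached at about 740 controls. With 125 evaluable patients, the limit with unlimited controls is about 90%.

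**Liver-volume difference detectable with 90% power at 1:1.**

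- 120 v 120: 0.4202 × 0.289 = 0.121 L
- 150 v 150: 0.3755 × 0.289 = 0.109 L

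The pooled mean implied by the plan is 0.084 / 0.06 = 1.4 L, so these are 8.7% and 7.8% of the mean rather than 6%.

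**Expected 95% CI half-width at 1:1.**

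- 120 v 120: 1.970 × 0.289 × √(2/120) = 0.073 L
- 150 v 150: 1.968 × 0.289 × √(2/150) = 0.066 L

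Both are close to the 0.084 L target.

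**The case against.** The protocol never says 1:1. Controls come from existing data and cost no enrolment, so a larger ratio is quite possible; with 150 evaluable patients and ten controls each, liver volume would have 92.4% power. There is also a reading, unlimited controls with drop-out applied as × 1.2, that yields 150 for liver volume. On it, 150 would have been set by the most demanding endpoint, and cT1 and PDFF would be more than covered. The comparison needs only the baseline scan at Visit 2, and withdrawn participants are replaced, so losing a full 20% before that scan is the pessimistic case. Liver volume is one item within one secondary endpoint, and Section 10.2 reports estimation rather than tests alone: "The results will be expressed as effect sizes and 95% confidence intervals (95% CI".

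Much of this stands. Liver volume is not underpowered under every design, and the 61% to 71% range belongs to 1:1 matching. But none of it makes the three identical statements true. The reading that rescues liver volume needs unlimited matched controls and a non-standard inflation, neither of which is stated, and it does not make 150 the requirement for cT1 or PDFF. Section 6 itself budgets for 20% drop-out, so 120 evaluable cannot be set aside. Nor can this be left to an SAP, because the figures at fault stand in the protocol. Reporting confidence intervals limits the harm but does not correct a stated power.

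**Conclusion.** The concern holds. Using the plan's own differences and SDs, n=150 cannot be the 90% requirement for all three metrics at any common control ratio. As a number of patients it is ample for cT1 and sufficient for PDFF at 1:1. For liver volume the stated 90% is not reached at one to four controls per patient, whether 120 or 150 patients are evaluable. It is reached only if all 150 are evaluable and each has at least about five controls.

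The size of the shortfall rests on two things the protocol leaves open: the control ratio, which is assumed here and shown as a range, and whether drop-out or replacement sets the evaluable number. The primary comparison is not at risk. This should be fixed, but it does not threaten the study's main conclusion.

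**What to change.** In Section 6:

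1. State that 150 is the number of patients with type 2 diabetes.
2. State the planned number of matched controls per patient.
3. State whether the evaluable number at the baseline scan is 120 (20% drop-out) or 150 (replacement under Section 7.3.3).
4. Replace the three identical claims with the power for each endpoint on that basis. If the plan is 120 v 120, for example, these are cT1 99.5%, PDFF 93% and liver volume 61%.
5. For liver volume, either give the difference detectable with 90% power (0.121 L at 120 v 120, 0.109 L at 150 v 150), or keep 0.084 L at 90% on condition of 150 evaluable patients and at least about five matched controls each (750 controls give 90.1%), after confirming that the existing data can supply them.
6. Editorially, correct the label that calls the 0.289 L SD a pooled mean.

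The cost is wording and recalculated figures. Any extra controls come from existing data, so no new enrolment is needed; the price of not using them is a lower stated power for liver volume.

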7. STUDY PROCEDURES

7.1. Recruitment

Participants will be identified from the community, primary care and secondary care diabetes; appointments; specifically, those patients with type 2 diabetes who are prescribed glucose lowering treatment as per their standard of care. A member of the clinical care team will provide potential participants with a study invitation letter and an accompanying Participant Information Leaflet (PIL) in the following places:

- 1) Liverpool Diabetes Partnership/ Aintree University Hospital (Liverpool University Hospitals NHS Foundation Trust)
- 2) The Oxford Centre for Diabetes, Endocrinology and Metabolism (OCDEM) based at the Churchill Hospital, the Horton Hospital and the John Radcliffe Hospital (Oxford University Hospitals NHS Foundation Trust)
- 3) The Royal Free London NHS Foundation Trust - Diabetes Department
- 4) Perspectum Ltd., Oxford

At each locality (Oxford, Liverpool, London catchment area of Royal Free NHS Foundation Trust), posters will be displayed around the hospitals, University departmental buildings and GP practices so that potential participants can also self-refer into the study by contacting the study team directly. The study will also be advertised on social media platforms (for example, Twitter and Facebook), Perspectum Ltd.'s website, hospital websites, newspapers and the Diabetes UK Patient Online Forum (forum.diabetes.org.uk). iWantGreatCare Ltd., a company that operates a patient experience data collection and analysis service, will also advertise the study by sharing the study poster via their website and will provide a website link to the Perspectum webpage for patients interested in participating in this research. The Perspectum webpage will provide a copy of the advertisement with details of how to contact us for further information.

A short film outlining the use of ATLAS in Perspectum's research will also be made available on Perspectum's MODIFY website and other social media platforms. We also plan to recruit through health awareness sessions in the local hospitals. Once a potential participant has been identified by any of these means and has expressed an interest in taking part in the study, they will be sent a Participant Information Leaflet (PIL) to read. They will be allowed as much time as they require to understand the details of the study and what's involved. Further to this, they will be given the opportunity to discuss the study with a member of the research team as part of the informed consent process.

7.2. Informed Consent

The participant must personally sign and date the latest approved version of the Informed Consent Form (ICF) before any study specific procedures are performed. This can be obtained via a hard copy or via the online consent platform that will be available to further prevent the spread of COVID-19.

Written and verbal versions of the Participant Information Leaflet (PIL) and Informed Consent Form (ICF) will be presented to the participants detailing no less than: the exact nature of the study; what it will involve for the participant; the implications and constraints of the protocol; and any risks involved in taking part. It will be clearly state that the participant is free to withdraw from the study at any time and for any reason without prejudice to future care, and with no obligation to give the reason for withdrawal.

The participant will be allowed as much time as wished to consider the information, and the opportunity to question the Investigator, the research team, their GP or other independent parties to decide whether they will participate in the study. Written Informed Consent will then be obtained by means of participant dated signature using the paper version of the Informed Consent Form or by using the online platform for obtaining Informed Consent. This will be followed by a dated signature of the person from the clinical study team who presented and obtained the Informed Consent.

7.3. Study Visits

In addition to the screening visit, there will be three dedicated study visits that are in addition to standard care for the participants. As far as possible we will endeavour to align study visits with clinic appointments or combine early visits, for the participants' convenience. As a precautionary measure and in an effort to prevent the further spread of COVID-19, participants will be asked to confirm whether they have experienced any of the documented symptoms prior to each study visit. Participants may also undergo a temperature measurement if necessary.

Appointments will be allocated to specific time slots to ensure minimal contact between staff and participants and so social distancing measures can be adhered to where possible. Social distancing will not be possible during some study assessments, such as blood tests.

Personal protective equipment (PPE) should be worn by all study staff in accordance with Public Health England guidance. This could include the use of items such as a plastic apron tied securely at the back, a surgical mask covering the nose, mouth and chin, and gloves. Suitable PPE can also be offered to participants, with special consideration for equipment used during imaging appointments. For example, ensure the metal strip is removed from the nose piece of surgical masks and replaced with tape, as per the guidance example in Appendix 1.

Table 1 illustrates what will happen at each study visit. Day 0 (Baseline) is defined as the day that the consented patient attends their diabetes clinic in order to participate in the study.

Activities	Screening visit	Visit 1: Baseline, Day 0	Visit 2: Within 21-days of Visit 1	Visit 3: 6-9 months after Visit 1	Follow Up phase at 1 year, 3 years and 5 years
Informed Consent	X				
COVID-19 check	X	X	X	X	X
Medical Record Review	X				
Concomitant Medication Check	X				
Medical History		X		X	
Anthropometrics		X		X	
Blood Sample		X		X	
Urine Sample		X		X	
Multiparametric MRI Scan			X	X	
Echocardiogram (optional)			X		
Medical Record Data Collection		X	X	X	X
Potential supplementary phone call to participant to: - clarify data that may not be clear from medical record -fill in missing data from medical record; -In case of Perspectum- recruited participants who have consented to medical record check, to complete Yrs 1,3,5, follow-up data collection					X
Patient Reported Outcome/Experience		X	X	X	

Measures (PROMs)/PREMs)					
Clinician Reported Experience Outcomes				X	

Table 1 - Study visits and measurements

7.3.1. Standard study visit – assessments

Medical history (~10 min)

We will obtain a full medical history including age, diabetes presentation, diabetes complications, diabetes duration, previous and current diabetes medication, current medication regime, family history, smoking history, alcohol history, ethnicity, history of cardiovascular disease, QRISK score, history of kidney disease, history of liver disease and record of any other co-morbidities the patient may have.

We will confirm that the participant has no contraindications for MRI (e.g. pregnancy, pacemaker or other metallic unfixed implanted device, metallic fragments, extensive tattoos, severe claustrophobia, metal in clothing). A resting blood pressure measurement will be taken.

All measurements will be recorded on the study participant’s Case Report Form (CRF).

Anthropometric measurements (5 min)

We will measure the height and weight of the participant to calculate BMI and also take hip and waist circumference.

Blood sample (10 min)

Routine bloods will be performed as per standard-of-care for T2D or its complications and will include: HbA1c, serum creatinine, electrolytes, lipids, FBC (full blood count), LFT (liver function tests that include aspartate transaminase and alanine transaminase) and gamma glutamyl transferase (GGT). eGFR will also be calculated.

A further blood sample of approximately 10 ml will be taken to measure additional circulating biomarkers [such as the enhanced liver fibrosis test (ELF), N-terminal levels of type III procollagen (P3NP), pancreatic lipase, cystatin C, serum albumin, high sensitivity C-reactive protein, NT-proBNP and uric acid] and optional genetic testing for NAFLD or T2D associated genetic variants. Consent for genetic testing and to place blood samples in the biobank at Liverpool, Royal Free London or Oxford for future testing will be optional for all participants for up to 7 years after baseline to enable evaluation after full study completion.

Biomarker	Key organ(s)
HbA1c	Various/pancreas
Lipids	Various
GGT	Liver (various)

Full Blood Count	Various
LFT, including AST and ALT	Liver
Serum Creatinine	Kidney
Urine Albumin Creatinine Ratio	Kidney
Electrolytes	Kidney

Table 2 - Standard of care circulating biomarkers in study

Urine sample (10 min)

Routine urine sample collection will be performed as per standard of care to measure urine dipstick and urine albumin creatinine ratio.

MRI Scan (~30min)

All participants will undergo a standardised imaging protocol (ATLAS) in an MRI scanner. At the time of initial consent, participants will be asked for their consent to have their images de-identified and stored. The MRI scan is not painful or risky, but a small minority of people feel claustrophobic. If this is apparent during screening, we will advise the patient to not participate. If this becomes apparent during a scan, we will stop the scan and take them out.

The MRI scans will be performed exclusively for research purposes and are not routinely looked at by a clinician. If a study investigator suspects an incidental finding, then they will follow the Perspectum Ltd incidental findings standard operating procedure (please refer to section 13.1 of this protocol). Blood pressure measurement may be taken at the same visit.

OPTIONAL Echocardiogram (~30min)

Participants may undergo a standardised transthoracic echocardiogram (ECHO) protocol using an ultrasound machine at visit 2. Participants will be asked for their consent to have de-identified images stored at the time of initial consent. The ECHO scans will be performed exclusively for research purposes and are not routinely looked at by a clinician. If a study investigator suspects an incidental finding, then they will follow the University of Liverpool incidental findings standard operating procedure.

Patient reported experience and outcome measures (~10min)

All participants will be asked to complete a questionnaire on a hand-held tablet at the end of all active study visits (or on their mobile phone/online). They will be asked to describe their experience within the clinical care setting and the impact of their prescribed treatment course.

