
4. To assess changes in multiple organs (liver, kidneys, pancreas, spleen and aorta) that occur over 6-9 months, with conventional biochemical biomarkers utilised in the clinical pathway for T2D, chronic kidney disease (CKD) and non-alcoholic fatty liver disease (NALFD).
	
4. 6-9 months: difference from baseline across the cohort in the following metrics:
 
 glycaemic control (HbA1c) lipid profiles renal health (serum creatinine, eGFR, urine albumin-creatinine ratio) liver health (FBC, LFT).

5. To evaluate the impact of multi-parametric abdominal MRI on type 2 diabetes management.
	
5. Review/analysis of patient and clinician reported outcome measures collected from non-validated questionnaires.

6. To determine the prognostic information provided by abdominal imaging for longer-term evaluation of clinical outcomes (after 1, 3 5 years).
	
6. At 1, 3 and 5 years: odds ratio for developing cardiovascular, liver, pancreatic and kidney related events and/or death, including hospital admissions.

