4. STUDY DESIGN

a. Study Description

This will be a multi-site study adopting a prospective, observational, longitudinal, cohort study design. There will be no intervention to the standard of care. Participants will be required to attend a screening visit and additional study visits on up to three time points – baseline (visit 1), a visit within 35 days of baseline (visit 2) and at 6-9 months (visit 3). The second and third visit will involve having a multiparametric MRI scan. Where possible some visits (the screening visit 1 or visit 1 /visit 2) may be on the same day or within standard of care, depending on patient and MRI scanner availability. The screening visit may be able to take place remotely over the phone, depending on the preference of the participant and the study team, facilitated by the use of an online platform to obtain Informed Consent. In consideration of the COVID-19 pandemic, prior to each study visit, participants will be asked to confirm whether they have experienced any

of the documented symptoms. Participants may also undergo a temperature measurement at the discretion of the local clinical care team.

Patients with type 2 diabetes and prescribed with glucose lowering therapy (as per standard of care) will be recruited from community settings, primary care centres and diabetes clinics within secondary care settings (see Fig. 3). We aim to recruit patients who have been newly prescribed medication; also, those patients undergoing treatment intensification (when an additional treatment is being considered due to evidence of poor glycaemic control), as per their standard of care HbA1c level results. Clinical outcome measurements, blood samples and urine samples will be collected to assess the response to standard of care treatment. There will be an optional thoracic echocardiogram (ECHO) included at visit 2. This is a non-invasive way in which we can capture data to enable us to assess cardiovascular disease.

Study participants will be enrolled in this study for a total of 5-years. During this time, consented participants will be asked to attend for up to 3 study visits: Visit 1 (baseline), Visit 2 and Visit 3.

Visit	Time	Visit Details
Screening visit	0 weeks	
 ● Informed Consent ● Medical Record Review

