9. INTERVENTIONS

There will be no intervention to the standard of care these patients receive. However, consented participants will be asked to make two study visits where a multiparametric MRI scan will be performed – these visits will be defined as visit 2 and visit 3. An optional echocardiogram may be included at Visit 2. The example guidelines provided in Appendix 1 should be taken into consideration when imaging research participants to ensure the safety of both staff and participants, whilst helping to further prevent the spread of COVID-19.

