12.7. Expenses and Benefits

Reasonable travel expenses for all study specific visits (outside of standard of care) that are additional to normal care will be reimbursed on production of receipts, or a mileage allowance provided as appropriate. Expenses will also be provided for one companion, if applicable.

Participants will receive a formal letter of thanks and study feedback after completion of their last face-to-face visit, and around the time of their 1-year follow-up. The letter will provide details on study progress, recent study publications and some basic healthy lifestyle guidance. A copy of a participant's LiverMultiScan Reports from baseline and 6-9-month follow-up MRI scans will also be included, with guidance on how to interpret the metrics of cT1 and PDFF.

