13. OTHER ETHICAL CONSIDERATIONS

13.1. Incidental findings

Scans are carried out for research purposes only and are not a replacement for clinical diagnosis. In addition, existing disease may not be detected. If a suspected incidental finding is discovered, scans (MRI or optional ECHO) will be screened for technical artefacts by a relevantly trained specialist and where a perceived incidental finding is noted, it will be managed following the investigation-specific Incidental Findings Management Plan. If a site or local imaging facility has a bespoke Incidental Findings Management Standard Operating Procedure, this will be followed. In all other cases, Perspectum's Incidental Findings Management Plan will be followed, and the scans will be reviewed by an expert reviewer (a radiologist) to assess for clinical significance. In the event that a potentially clinically significant incidental finding is discovered, this will be communicated to the relevant site's Principal Investigator who will discuss this with the participant and, if appropriate, the finding will be referred to their GP and/or specialist consultant for further investigation as necessary.

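### Secondary objective 5 claims to evaluate the impact of MRI on diabetes management, but the design can show only experience and perceived usefulness

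*Protocol*

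**What the plan says.** The Synopsis and Section 3 give secondary objective 5 as "To evaluate the impact of multi-parametric abdominal MRI on type 2 diabetes management". Its outcome measure in Section 3 is "Review/analysis of patient and clinician reported outcome measures collected from non-validated questionnaires". No variable recording a management decision or a change of treatment is named for it.

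On who sees the scans, Section 7.3.1 says "The MRI scans will be performed exclusively for research purposes and are not routinely looked at by a clinician", and Section 13.1 adds "Scans are carried out for research purposes only and are not a replacement for clinical diagnosis". On care, Section 4 says "There will be no intervention to the standard of care", and Section 9 repeats the point.

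On timing, Table 1 (Section 7.3) marks the patient questionnaires at Visits 1, 2 and 3 and the clinician form at Visit 3 alone. Neither is marked in the follow-up phase at 1, 3 and 5 years. Section 12.7 has participants receive a letter "after completion of their last face-to-face visit, and around the time of their 1-year follow-up", enclosing their LiverMultiScan reports from both scans.

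On content, Section 7.3.1 says of the patient questionnaire: "They will be asked to describe their experience within the clinical care setting and the impact of their prescribed treatment course". The content of the clinician form is not described.

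**The concern.** To observe an impact of MRI on management, an MRI result must be available to someone who makes or influences a management decision, and the outcome must be recorded afterwards. The protocol provides for neither step in that order. Its questionnaires are complete by Visit 3, and the MRI metrics are released after Visit 3, to the participant.

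Section 2.1 says the study is meant to gather evidence of added value to the health service and to support later regulatory clearance. In that setting, a report that MRI had an impact on management would be read as evidence that results changed care. The data collected for objective 5 could not carry that meaning.

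**Working it through.** The plan gives no figure for objective 5, so there is nothing to reproduce. The check is the order of events and the flow of information.

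**Step 1: order of events**

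| Event | Time | Place in protocol |
|---|---|---|
| Visit 1: patient questionnaire | Day 0 | Section 4; Table 1 |
| Visit 2: first MRI, patient questionnaire | within 35 days (Section 4) or 21 days (Table 1) of Visit 1 | Section 4; Table 1 |
| Visit 3: second MRI, last patient questionnaire, only clinician form | 6 to 9 months | Section 4; Table 1 |
| Letter to participant with MRI reports | after Visit 3, around 1 year | Section 12.7 |

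The Visit 2 window differs between the two places, but either value gives the same order. The Visit 1 questionnaire also precedes the first scan, unless Visits 1 and 2 fall on one day, which Section 4 allows.

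**Step 2: gap between outcome and release.** Take around 1 year as month 12. The last objective 5 data arrive at months 6 to 9, so release follows by 12 − 9 = 3 to 12 − 6 = 6 months. If Section 12.7 is instead read as allowing a letter directly after Visit 3, the gap shrinks, but release still comes after the last questionnaire.

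**Step 3: routes from the scan to a treating clinician**

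- Clinical reading of the scan: not routine (Section 7.3.1).
- Report sent to the clinician: none described. The reports in Section 12.7 are enclosed in the participant's letter, and no copy to a clinician is mentioned.
- Incidental findings: these can go to the site's principal investigator and on to the GP or a specialist, possibly before Visit 3 (Section 13.1). They are exceptions, and they are not the quantitative multi-organ metrics that objective 5 concerns.

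**Step 4: what the instruments can show.** The stated content of the patient questionnaire is experience of care and the effect of treatment, not of MRI. The medical history at Visits 1 and 3 covers medication, so treatment changes could be described. They could not be attributed to MRI results that the protocol gives no clinician. The record reviews at 1, 3 and 5 years run to or past the letter, but they collect clinical events for objective 6.

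**Step 5: the protocol's own framing.** Section 2.1 presents ATLAS as a technique under development that will feed a decision support tool in the future. That places MRI-guided management after this study.

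**The case against.** The strongest reply is that the clinician form cannot be seen. It is the instrument closest to management, and a single form after the baseline scan fits a survey of perceived usefulness. Section 2.1 states a matching aim, to assess what MRI metrics add to patient pathways. Endpoint 5 itself claims only to review questionnaire responses, with no hypothesis or effect attached. This stands. It limits the point to observed impact, and it means that the objective's wording is at fault more than the endpoint's.

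Some passages also say less than they might seem to. The sentence on clinicians not routinely looking at scans introduces the rule on incidental findings and does not expressly bar sharing derived metrics. Leaving standard care unaltered means that the study imposes no treatment; it does not say that MRI information had no influence. Section 12.7 does not say that the letter is the only release. So the finding is that no earlier route is provided, not that one is forbidden.

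A reader might go further and infer that objective 5 cannot be answered in any form, or that no participant's care could have been touched by MRI. The documents support neither inference: perceived usefulness can be collected, incidental findings may reach a clinician, and silence about disclosure cannot be turned into a count. A reader might also fault the absence of a group managed without MRI. That is a feature of a single-cohort observational design, and endpoint 5 promises no comparison.

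**Conclusion.** The point holds for observed impact. As written, objective 5 promises something that the described flow of information and timing of collection cannot deliver: no quantitative MRI result is provided to a treating clinician before the objective 5 data are complete. Patient and clinician experience, and perceived usefulness, remain within reach.

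The size is one of six secondary objectives. The primary endpoint, the sample size and the planned tests are untouched. The conclusion assumes that the protocol describes all planned disclosure of MRI metrics. An undocumented release to clinicians before Visit 3 would alter it, and would itself need to be written into the protocol. A statistical analysis plan could not close the gap, because the gap lies in who receives the results and when, not in how the responses are analysed.

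**What to change.** Reword secondary objective 5, in the Synopsis and Section 3, to patient and clinician experience and perceived potential usefulness of multi-organ MRI. State that no conclusion about actual impact on management will be drawn from it. Endpoint 5 already describes what is collected and needs little change. The cost is a wording amendment and a more modest claim; no visit, participant or procedure is added.

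Optionally, the clinician form could ask whether the MRI report would have changed a management decision already recorded. This costs more than a wording change, because showing the report is a new disclosure step. The protocol would have to state when the report is shown and reconcile that with the research-only use of scans (Sections 7.3.1 and 13.1) and with unaltered care (Sections 4 and 9). It should also say who completes the form at the non-NHS site, where Section 7.3.2 says staff cannot reach medical records. Answers should be reported as hypothetical change only.
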